Finally, Sucato noted a 1.2% ( $p>0.05$ ) difference in the proportion of patients taking no NSAIDs versus ketorolac undergoing spinal fusion with an overall incidence of 2.5%. Smokers made up 0.6% of the study population and none of them developed a nonunion. Among non-smokers, 1.9% Ketorolac users and 3.1% of controls had a nonunion ( $p>0.05$ ). The overall incidence among non-smokers was 2.5% (40).

To the authors' knowledge, only retrospective reviews evaluating the influence of ketorolac and delayed healing have been conducted in the clinical setting. As noted above, this includes both supportive and antagonistic evidence. Furthermore, ketorolac, as well as other NSAIDs have been primarily studied in spine surgery or studies dealing with traumas and high energy fractures. In all of the studies evaluating NSAIDs and post-operative bunionectomy pain, bone healing was not evaluated, nor reported as a significant adverse event. This is an important distinction to note, since bunion correction involves long bone healing while spinal surgery entails irregular bone healing. Bunionectomy procedures also involve making a controlled osteotomy cut which may biologically vary substantially from traumatic and fusion of two independent bones as is the case with spine arthrodesis.

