### **C. Preliminary Studies/Pilot Data**

Review of the investigators' sites revealed that the Kalish bunionectomy has been in use for over 15 years. Ketorolac has been intermittently and randomly administered to patients for approximately ten years. Given there are no contra-indications or dosage adjustments, patients may be given 30 mg intra-venous near the end of surgical case. Patients then begin taking 10 mg orally, every 8 hours for a total of five days post-operatively.

Additional pilot data was undertaken at one of the investigators' outside sites (Mount Auburn Hospital, Cambridge, MA). An IRB approved retrospective chart review evaluated the outcomes of a bunionectomy procedure. Within this study, we determined the incidence of nonunions following a Lapidus bunionectomy. Some of these patients also received ketorolac (30 mg IV intra-operatively, then 10 mg orally for a total of five days). There were 29 patients that underwent a modified Lapidus bunionectomy with at least two lag screws, in 2007-2008 that were also given ketorolac for pain control. Radiographs were assessed for nonunions by utilization of a previously documented scoring

system found to have both high inter- and intra-observer reliability in a series of tibial fractures reduced surgically with serial radiographs. This scoring system grades each fracture according to four characteristics: 1. Rating of fracture healing, 2. Callus morphology, 3. Number of cortices visible or obliterated. 4. Number of cortices bridged (41). The modification utilized for this pilot data was as follows:

- ❖ **Grade 1:** Homogenous bone structure with complete obliteration of fusion site
- ❖ **Grade 2:** Massive bone trabeculae crossing fusion site, 3-4 cortices are bridged with fusion site barely discernable
- ❖ **Grade 3:** Apparent bone trabeculae crossing fusion site, 2-3 cortices are bridged with fusion site discernable
- ❖ **Grade 4:** Trace bone trabeculae crossing fusion site, 1-2 cortices are bridged with distinct visible joint space
- ❖ **Grade 5:** No bone trabeculae crossing fusion site, 0 cortices are bridged with complete visible joint space

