The patient diaries with the VAS will be collected during the first post-operative visit (one week). Patients will be asked to bring all surgery related medications and bottles to this post-operative appointment. The research fellow will again obtain the patient's post-operative pain medication consumption (including timing and dosages) by counting pills and verbally confirm study protocol compliance (Please refer to the variables collected section for full details).

Whether a difference in delayed unions at twelve weeks exists between the two groups will also be assessed. Radiographic union for each patient will be assessed by both a blinded, board-certified radiologist and two blinded board-certified podiatric surgeons. Agreement between these three experts will be assessed with a kappa score and the mean result will be used for primary analysis. Delayed and non-union rates will be compared between the two groups. A previously documented scoring system found to have both high inter- and intra-observer reliability in a series of tibial fractures reduced surgically will be utilized for this assessment. This scoring system grades each fracture according to four characteristics: 1. Rating of fracture healing, 2. Callus morphology, 3. Number of cortices visible or obliterated. 4. Number of cortices bridged (41). The modification utilized for this study will be as follows:

- ❖ **Grade 1:** Homogenous bone structure with complete obliteration of fusion site
- ❖ **Grade 2:** Massive bone trabeculae crossing fusion site, 3-4 cortices are bridged with fusion site barely discernable
- ❖ **Grade 3:** Apparent bone trabeculae crossing fusion site, 2-3 cortices are bridged with fusion site discernable
- ❖ **Grade 4:** Trace bone trabeculae crossing fusion site, 1-2 cortices are bridged with distinct visible joint space

- ❖ **Grade 5:** No bone trabeculae crossing fusion site, 0 cortices are bridged with complete visible joint space

A delayed-union will be defined as a grade 4 or 5 in any patient over twelve weeks. A nonunion will be defined as a grade 4 or 5 in any patient over six months. Analysis will include logistic regression for these binary endpoints. Odds ratios and 95% confidence intervals will be calculated between groups (delayed and/or non-union: yes/no). A 2-sided p value of  $\leq 0.05$  will be considered statistically significant.

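### The cortex ranges of grades 3 and 4 overlap at the cut that defines delayed union and nonunion, and the line descriptors that should separate them are worded for a joint fusion, so some two-cortex films can be scored either way

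*Combined protocol and SAP*

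**What the plan says.** Section B3.B.b (Data Analysis, Outcomes and their Measurements, a. Primary Outcome) sets out five radiographic grades, and four of them carry a cortex count. The second grade allows three or four bridged cortices and the fifth none. The two grades on either side of the event cut are worded as follows:

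- Not counted as an event (the third grade, two or three cortices): "Apparent bone trabeculae crossing fusion site, 2-3 cortices are bridged with fusion site discernable"
- Counted as an event (the fourth grade, one or two cortices): "Trace bone trabeculae crossing fusion site, 1-2 cortices are bridged with distinct visible joint space"

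Delayed union is set by this rule: "A delayed-union will be defined as a grade 4 or 5 in any patient over twelve weeks". Nonunion uses the same two grades at the later time point: "A nonunion will be defined as a grade 4 or 5 in any patient over six months". One radiologist and two podiatric surgeons, all blinded, read the films. Their agreement is summarised by kappa, and the mean of their results enters the primary analysis. The event is then analysed as yes/no by logistic regression.

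The same five grades appear word for word in B2.C (Preliminary Studies/Pilot Data), where the operation was different: "Within this study, we determined the incidence of nonunions following a Lapidus bunionectomy". Section A.3 describes the trial operation as a V-shaped cut through the first metatarsal, fixed with screws. The protocol draws the contrast itself in B2 (Clinical Studies Overview): "Bunionectomy procedures also involve making a controlled osteotomy cut which may biologically vary substantially from traumatic and fusion of two independent bones".

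Section A.4.h gives a second definition. It classifies delayed union and nonunion by whether osseous union is incomplete at the two time points, and it mentions no grade.

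**The concern.** The boundary between grades 3 and 4 is the only one that decides whether a patient counts as an event, and the cortex ranges overlap there. The descriptor of how visible the line is could have broken the tie. For grade 4 it asks for a joint space, which is absent at the healing site of an osteotomy within one bone. No rule says which descriptor prevails when they disagree.

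Pain at 48 hours is the primary outcome of interest, but bone healing is the trial's main safety question. It has its own sample-size calculation (B3.B.a) and appears under the Primary Outcome heading. If readers place the same kind of film on different sides of the cut, the endpoint carries avoidable noise. In a comparison where a null result may be read as no harm to bone, that noise matters.

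The classification can also affect follow-up, because A.7 ties the end of a patient's participation to radiographic union at twelve weeks on this scale.

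**Working it through.** **1. Cortex count to grade to event.** Each count from 0 to 4 was assigned to every grade whose printed range contains it (grade 1 gives no count).

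| Bridged cortices | Grade(s) | Event (grade 4 or 5)? |
|---|---|---|
| 0 | 5 | yes |
| 1 | 4 | yes |
| 2 | 3 or 4 | no or yes |
| 3 | 2 or 3 | no |
| 4 | 2 | no |

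Two cortices is the only count whose event status is not fixed. The overlap at three cortices has no effect on the event.

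**2. Do the other descriptors settle it?** Grades 3 and 4 also differ in trabeculae (*apparent* against *trace*) and in line visibility. The trabecular wording does not depend on the fusion language and can separate clear cases, but neither word is quantified. The line descriptor is worded for a fusion, and titles in the protocol's reference list call the Lapidus procedure an arthrodesis. What stays open is the set of two-cortex films whose trabecular and line descriptors are borderline or in conflict.

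**3. Does the mean of three readers settle it?** Readings of 3, 3, 4 give 10/3 = 3.33, and 3, 4, 4 give 11/3 = 3.67. Neither is a defined grade, and no cut is stated for values between 3 and 4.

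**4. The two definitions side by side.** A grade 3 film at twelve weeks, with a discernible line and two or three cortices bridged, is not a delayed union under B3.B.b. Under A.4.h it could be called incomplete union and so a delayed union.

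**5. Size.** The documents give neither the share of two-cortex films nor a control event rate, so the following is an illustration on assumed rates.

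The plan's own figure comes first. B3.B.a gives 38 per arm for a 20.5-point difference, two-sided 0.05, 80% power. With the pooled two-proportion formula, n = [1.96·√(2p̄(1−p̄)) + 0.842·√(p₁(1−p₁)+p₂(1−p₂))]²/d², an assumed control rate of 1% gives 37 and 2% gives 39. The stated 38 is therefore consistent with a control rate of about 1–2%. The point here does not depend on that figure.

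Assume true rates of 1% (placebo) and 21.5% (ketorolac), 44 read per arm, and a fraction f of non-event films recorded as events, at random and equally in both arms. The observed rate is p + (1−p)f.

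| f (assumed) | Observed rates | Power, 44 per arm |
|---|---|---|
| 0 | 1.0% vs 21.5% | 87% |
| 5% | 6.0% vs 25.4% | 72% |
| 10% | 10.9% vs 29.4% | 58% |
| 20% | 20.8% vs 37.2% | 39% |

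At f = 10% the odds ratio moves from (0.215/0.785)/(0.01/0.99) = 27.1 to (0.2935/0.7065)/(0.109/0.891) = 3.4. In the other direction, if 25% of true events are recorded as grade 3 and f = 0, the rates are 0.75% and 16.1% and power is about 75%.

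**The case against.** Several points on the other side stand.

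- A reader might infer that every two-cortex film is undetermined. The text does not support this, because the grades combine several descriptors and the trabecular one separates some of these films.
- A reader might infer that one person's judgement decides the endpoint. It does not: three blinded readers are pooled. Pooling limits the problem but does not define the event, and kappa would measure disagreement without resolving it.
- A reader might infer that the odds ratio must be pulled towards 1, giving false reassurance on safety. That needs inconsistent assignment. If all readers put two-cortex films on the same side, the threshold only moves, and if ketorolac slows healing the contrast could even grow. Dilution is a tendency to the extent that readers differ.
- The pilot used the same grades and the same cut, and two independent surgeons agreed on one nonunion in 29 (1/29 = 3.45%). This is the only evidence in the documents on how the modified scale performs. It is small, comes from a fusion, and reports agreement on the event rather than on the grades. The high reliability cited for the parent scale comes from tibial fractures.
- Letting the cortex count override everything else would be a choice that the documents do not justify over the alternatives.

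**Conclusion.** The point holds as a defect in a stated rule. Grades 3 and 4 share the two-cortex count at the event cut, and the line descriptors are worded for a fusion that this operation does not involve. Two-cortex films with borderline or conflicting descriptors can be scored as event or non-event. Where readers differ, this lowers kappa and would tend to dilute a between-arm difference in healing.

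The size is unknown. The power figures above rest on assumed event rates and on assumed random error equal in both arms; they show sensitivity and are not an estimate of what will happen in this trial. The documents do not support rating this as a must-fix: the 48-hour pain analysis is untouched and the harm to the union analysis cannot be quantified. It is a should-fix.

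**What to change.** Before any film is read:

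1. Make the cortex counts mutually exclusive, so that each count from 0 to 4 maps to one grade and two cortices falls on one named side of the 3/4 cut.
2. Replace the fusion-site and joint-space wording with osteotomy site or line in all five grades.
3. Agree with the readers, and write down, which descriptor decides when descriptors conflict.
4. Replace the mean result with the majority (two of three) event classification, so that values such as 3.33 or 3.67 cannot arise.
5. Reconcile the incomplete-union definition in A.4.h with the grade-based definition in B3.B.b.

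This is a change of wording and reader instructions; it needs no new films, patients or readers. The cost is some loss of comparability with the pilot series at the 3/4 boundary. Made after films have been read, the same choices would be post hoc.

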Nonunion was defined as grades 4 or 5. Nonunion analysis was performed by two independent foot and ankle surgeons. Both evaluators agreed that there was one nonunion out of 29 cases or 3.45%. This compares favorably with historical controls. According to prior literature, baseline nonunion rates (traditional Lapidus approach, no ketorolac reportedly given) for this procedure ranges between 0-12%, with higher nonunion rates occurring in older literature. It is believed that nonunion rates were higher in older literature due to the use of smaller screw sizes and antiquated surgical techniques (42-50). This pilot data implies that the addition of ketorolac did not appear to have adverse consequences with bone healing in this cohort of patients.

[figure not shown]

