The next consideration for study design is the sample size calculations for delayed and nonunion in each group. Because earlier calculations have already incorporated ICC assumptions, the previous approach is still considered appropriate. Again drawing from higher level studies, the difference to detect has been determined to be 20.5% between groups (38). Using the same criteria from the previous calculations, an 80% power to detect differences between groups with a 0.05 two-sided significance will require a total sample size of 76, or 38 subjects per arm. If the ICC were to be changed to 0.01 detection of a 20.5% difference requires 40 patients per group with five clusters of sixteen patients for the total of 80 subjects. Given the ICC assumptions of the VAS calculations the authors have already attempted to incorporate a highly conservative sample calculation and included a 10% inflation for drop-outs.

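### The union analysis names logistic regression but no sparse-data method, and at the nonunion rates quoted from other procedures an arm with no events is a realistic outcome

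*Combined protocol and SAP*

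**What the plan says.** In the combined protocol and SAP, B3 section B, Data Analysis, the union endpoints are described under the Primary Outcome heading. Delayed union is grade 4 or 5 beyond twelve weeks; nonunion is the same grades beyond six months. For both, "Analysis will include logistic regression for these binary endpoints", and "Odds ratios and 95% confidence intervals will be calculated between groups", with a two-sided 0.05 threshold. The estimation method is not stated, and nothing is said about small counts, empty cells or covariates in this model.

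Three other places bear on the point:

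- The Secondary Outcomes text gives binary data a chi-square comparison, 95% intervals and a Fisher exact p-value. It does not say whether this reaches the union endpoints.
- The Missing Data text counts patients lost from longer follow-up as treatment failures.
- The Sample Size Justification plans the union comparison on a 20.5-point difference, which "will require a total sample size of 76, or 38 subjects per arm". It states no control rate.

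On expected frequency, the Pilot Data section reports, for a different bunion operation (Lapidus): "Both evaluators agreed that there was one nonunion out of 29 cases or 3.45" per cent.

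**The concern.** Default logistic regression output is maximum likelihood with Wald tests and intervals. If one arm has no events, the likelihood keeps increasing as the coefficient moves away from zero. The odds ratio is then zero or infinite, the standard error is an artefact of where the iterations stop, and the Wald p-value drifts towards 1. If both arms are empty, the odds ratio is undefined.

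Bone healing is the concern the protocol gives for surgeons' reluctance to use ketorolac (Possible Benefits), and it has its own sample size calculation. An analysis that returns no interpretable estimate, or labels a one-sided excess of nonunions as far from significant, would fail on that question. A method chosen only after an empty cell has been seen is also open to the criticism that it was picked to suit the result.

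**Working it through.** **Inputs.** 44 per arm (Sample Size Justification). Nonunion rates, all from other procedures: 1/29 = 3.45% (Lapidus pilot, with ketorolac); 3.4% on ketorolac and 2.2% on control (2005 spinal-fusion study, non-smokers); 1.9% and 3.1% (adolescent scoliosis fusion study, non-smokers); 5.67% overall (spinal-fusion study that excluded smokers); 0 to 12% (historical Lapidus).

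**The plan's own figure.** The 38 per arm cannot be reproduced directly because no control rate is given. The pooled two-proportion formula is n = [1.96√(2p̄(1−p̄)) + 0.8416√(p₁(1−p₁) + p₂(1−p₂))]² / 0.205². For 2.0% against 22.5%, p̄ = 0.1225 and n = (0.9088 + 0.3707)² / 0.0420 = 38.95, so 39. Scanning the control rate gives 36 to 40 per arm for 0.9% to 2.2% (the unpooled form gives 37 to 40 for 2.0% to 3.1%). At 3.45% the pooled n is 43. The stated size therefore fits only a low control rate.

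**Chance of an empty arm.** With a = (1−p₁)^44 and b = (1−p₂)^44, P(at least one empty) = a + b − ab. The paired rows use the two arms' rates as quoted.

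| Rates assumed | Expected events per arm | At least one arm empty | Both empty |
|---|---|---|---|
| 3.45% in both | 1.5 | 38% | 5% |
| 2.2% and 3.4% | 1.0 and 1.5 | 51% | 8% |
| 3.1% and 1.9% | 1.4 and 0.8 | 57% | 11% |
| 5.67% in both | 2.5 | 15% | 0.6% |
| 12% in both | 5.3 | 0.7% | <0.1% |

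For the first row, 0.9655^44 = 0.213, and 2 × 0.213 − 0.213² = 0.381. With 40 evaluable per arm the first three rows become 43%, 56% and 62%.

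**Under the planned alternative.** Take the back-solved control rates and assume the 20.5 points are excess on ketorolac. Ketorolac then has 44 × 0.214 to 44 × 0.227 = 9.4 to 10.0 events and control has 0.4 to 1.0. The control arm is empty with probability 0.991^44 = 67% down to 0.978^44 = 38%.

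**What default output shows then.** For 10 of 44 against 0 of 44, a maximum-likelihood fit gave a standard error of about 12,000 and a Wald p of about 0.998; the exact value depends on where iteration stops. Fisher's test gives p = 0.001. For 6 against 0 the figures are about 0.998 and 0.026.

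**What sparse-data methods give.**

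- 2 against 0: Firth odds ratio (2.5 × 44.5)/(0.5 × 42.5) = 5.2; exact conditional 95% interval 0.19 to infinity; Newcombe risk difference −4.1 to +15.1 points.
- 6 against 0: Newcombe +2.8 to +26.7 points.
- 0 against 0: Newcombe −8.0 to +8.0 points.
- 2 against 1: maximum-likelihood odds ratio 2.05 (0.18 to 23.4); exact interval 0.10 to 124.

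**Losses counted as failures.** If a fraction d is lost, the event rate becomes d + (1−d)p. At 5% loss and p of 2.5% to 3.45%, the rate is 7.4% to 8.3%, with 3.2 to 3.6 events per arm and an empty-arm risk of 7% to 4%. At 10% loss the risk is below 1%.

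**The case against.** The case against has several sound parts.

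- **Rates.** None of the rates belongs to this operation. The pilot's 1/29 has an exact 95% interval of 0.1% to 17.8%. A spinal cohort with 48.9% smokers had 11.8%, and smoking is not among this trial's exclusions. At about 12% the problem nearly vanishes. This stands, so the size must be given as a range.
- **Delayed union.** A reader might infer that one or two events per arm are expected for both endpoints. The documents do not support this. They give no twelve-week rate, and with complete follow-up and no reversal of healing, grade 4 or 5 at twelve weeks cannot be rarer than at six months.
- **Losses.** The failure rule could fill most empty cells. It does so only with imputed events, however. The same text expects little missing data, and whether the rule covers the twelve-week endpoint is unclear.
- **Wording.** The plan does not say maximum likelihood or Wald, and Firth and exact versions are also logistic regression. This makes the fault one of under-specification, but default output remains a natural reading.
- **Fisher's test.** It is already named for binary data. If it reaches these endpoints, a valid p-value exists, but it does not supply the promised odds ratio interval.
- **Covariates.** None is listed for this model, and adjustment elsewhere is conditional, so separation caused by adjustment is only a possibility.
- **Information.** No method adds information, and the intervals stay wide. This stands.

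**Conclusion.** The gap is real: the union endpoints have an odds ratio analysis with no provision for sparse data. It matters most for six-month nonunion. If the rates of 1.9% to 3.45% quoted from other procedures apply with 44 followed per arm, an odds ratio of zero, infinity or undefined arises in about 38% to 57% of trials. That falls to 15% at 5.67% and under 1% at 12%, and is lower where losses are scored as failures. The low control rate implied by the plan's own sample size means the default test could also fail when harm is present.

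A reader might go further and say the trial will have no usable interval and no bound on harm. That is true only of the default Wald fit. With one empty arm an exact interval keeps one finite bound, and a score-based risk difference interval is finite throughout. For delayed union the risk cannot be sized from these documents. The point should be corrected before analysis, but it does not undermine the design.

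**What to change.** In the Primary Outcome text on union:

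1. Name Firth penalised logistic regression with a profile-likelihood interval, or exact logistic regression, with treatment as the only term, as the method for nonunion. Apply the same method to delayed union when events are few, with the threshold for few stated in advance.
2. State that the Fisher exact p-value in the Secondary Outcomes text also applies to both union endpoints.
3. Report the risk difference with a Newcombe or Miettinen-Nurminen 95% interval beside the odds ratio. Making it the main measure is optional.

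The cost is a few sentences of analysis text, with no change to data collection or sample size. The drawback is that the intervals will still be wide, because the limit is the number of events.
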